#### **4.6.1 Procedures for discontinuation of patient from IP**

At any time, patients are free to discontinue IP without prejudice to further treatment. A patient who decides to discontinue IP will always be asked about the reason(s) for discontinuation and the presence of any AEs. If possible, they will be seen and assessed by an investigator(s). AEs will be followed up (see Section 7).

Patients who are permanently discontinued from further receipt of IP, regardless of the reason, will be identified as having permanently discontinued treatment.

All patients will be followed for survival until the end of the study.

### **4.7 Criteria for withdrawal**

#### **4.7.1 Screen failures**

Screen failures are patients who do not fulfill the eligibility criteria for the study and therefore must not enter treatment. This reason for study withdrawal is only valid for screen failures (ie, not enrolled patients).

#### **4.7.2 Withdrawal of the informed consent**

Patients are free to withdraw from the study at any time (IP and assessments) without prejudice to further treatment.

Patients who withdraw treatment in the study will not receive further IP, with the exception of follow-up for survival, which will continue until the end of the study unless the patient has expressly withdrawn their consent.

##### **4.7.2.1 Survival status for patients who withdrew consent and were lost to follow-up**

Patients will be considered lost to follow-up only if no contact has been established by the time the study is completed, such that there is insufficient information to determine the patient's status at that time. Patients who refuse to continue participation in the study, including telephone contact, should be documented as "withdrawal of consent" rather than

“lost to follow-up.” Investigators should document attempts to re-establish contact with missing patients throughout the study period. If contact with a missing patient is re-established, the patient should not be considered lost to follow-up and evaluations should resume according to the protocol.

At the time of PFS and OS analyses, the survival status of all patients should be re-checked; this includes those patients who withdrew consent or are classified as “lost to follow-up.”

- Lost to follow-up: site personnel should check hospital records, the patients’ current physician, and a publicly available death registry (if available) to obtain a current survival status.
- In the event that the patient has actively withdrawn consent to the processing of their personal data, the survival status of the patient can be obtained by site personnel from publicly available resources where it is possible to do so under applicable local laws to obtain a current survival status. (The applicable CRF modules will be updated.)

## **5 STUDY PLAN AND TIMING OF PROCEDURES**

This study has been subject to an internal review according to AstraZeneca standard procedures.

The latest version of the IB and any subsequent updates will be supplied to the investigator. Investigators need to become familiar with the content of the IB and appendices associated with this protocol.

Patients may delay dosing under certain circumstances.

- Dosing may be delayed per Toxicity Management Guidelines, due to either an immune or a non-immune-related AE.
- If dosing must be delayed for reasons other than treatment-related toxicity, dosing will resume as soon as feasible.
- For subsequent cycles the time between 2 consecutive doses cannot be less than 21 days, based on the half-lives of durvalumab. If there is a dosing delay while on the q3w schedule, all future dosing days should be delayed to ensure that the intervals between dosing study treatment are always at least 21 days.

Table 2 below outlines data collection measures that are considered for this study.

**Table 2 Schedule of assessments**

| Visit   | Screening                | Treatment period         |  |  | Safety follow-up visit         | Survival follow-up phone calls/emails |
|---|--------------------------|--------------------------|--|--|--------------------------------|---------------------------------------|
|   |                          | Baseline (Day1, Cycle 1) | During Chemotherapy
1 cycle = 21 days | Post-Chemotherapy
1 cycle = 28 days |                                |                                       |
| window                                       | Day-28 to Day-1   | 0                 | ±3 days                           | ±3 days                         | ±7 days                 | ±14 days                       |
| Week   | Weeks-4 to Week-1 | Week 0            | [REDACTED]                        | [REDACTED]                      | 90 days after last dose | Every 3 months                 |
| Written informed consent a               | X                        |                          |  |  |                                |                                       |
| Inclusion/exclusion criteria                        | X                        |                          |  |  |                                |                                       |
| Demographics, including baseline characteristics    | X                        |                          |  |  |                                |                                       |
| Medical history, including cancer treatment history | X                        |                          |  |  |                                |                                       |
| ECG recording b                          | X                        | As clinically indicated  |  |  |                                |                                       |
| Physical examination, weight, and vital signs       | X                        | X                        | X  | X                                      | X                              |                                       |
| Concomitant medications                             | X                        | X                        | X  | X                                      | X                              |                                       |
| Laboratory Assessments                       |                          |                          |  |  |                                |                                       |
| Clinical chemistry c                     | X                        | X d           | X  | X                                      | X                              |                                       |
| Hematology c                             | X                        | X d           | X  | X                                      | X                              |                                       |
| TSH, (reflex free T3 or free T4 f )      | X                        | X e           | X  | X                                      | X                              |                                       |

| Visit  | Screening                | Treatment period   |  |  | Safety follow-up visit         | Survival follow-up phone calls/emails |
|--|--------------------------|--|--|--|--------------------------------|---------------------------------------|
|  |                          | Baseline (Day1, Cycle 1)   | During Chemotherapy
1 cycle = 21 days | Post-Chemotherapy
1 cycle = 28 days |                                |                                       |
| window  | Day-28 to Day-1   | 0   | ±3 days                           | ±3 days                         | ±7 days                 | ±14 days                       |
| Week  | Weeks-4 to Week-1 | Week 0  | [REDACTED]                        | [REDACTED]                      | 90 days after last dose | Every 3 months                 |
| Hepatitis B, C, HIV virology   | X                        |  |  |  |                                |                                       |
| Pregnancy test g  | X                        | X  | X  | X                                      | X                              |                                       |
| Urinalysis   | X                        | As clinically indicated  |  |  |                                |                                       |
| Monitoring  |                          |  |  |  |                                |                                       |
| AE   | X                        | X  | X  | X                                      | X                              |                                       |
| ECOG performance status  | X                        | X  | X  | X                                      | X                              |                                       |
| IP Administration   |                          |  |  |  |                                |                                       |
| Durvalumab h  |                          | X  | X  | X                                      |                                |                                       |
| Etoposide i   |                          | X  | X k                           |  |                                |                                       |
| Carboplatin or cisplatin ij   |                          | X  | X k                           |  |                                |                                       |
| Tumor assessment per Investigator - report (according to RECIST1.1) l | X                        | On study tumor assessments should occur at Week 6±2 weeks, at Week 12±2 weeks then every 8±2 weeks m until PD |  |  |                                |                                       |
| Subsequent anticancer therapy  |                          |  |  |  | X                              | X                                     |
| Survival status  |                          |  |  |  | X                              | X                                     |

a. Written informed consent and any locally required privacy act document authorization must be obtained prior to performing any protocol-specific procedures, including screening/baseline evaluations. If laboratory or imaging procedures were performed for alternate reasons prior to signing consent, these can be used for screening purposes with

consent of the patient. However, all screening laboratory and imaging results must have been obtained within 28 days of first dose.

- b. Any clinically significant abnormalities detected require triplicate ECG results.
- c. Serum or plasma clinical chemistry (including LFT monitoring) and hematology may be performed more frequently if clinically indicated.
- d. If screening laboratory assessments are performed within 3 days prior to Day 1 (first infusion day), they do not need to be repeated at day 1.
- e. If TSH is measured within 14 days prior to Day 1 (first infusion day), it does not need to be repeated at Day 1.
- f. Free T3 or free T4 will only be measured if TSH is abnormal or if there is clinical suspicion of an AE related to the endocrine system.
- g. Pregnancy test will be performed in women of childbearing potential only. A urine or serum pregnancy test is acceptable. Women of childbearing potential are required to have a pregnancy test within 7 days prior to the first dose of study drug and then every 3 weeks during chemotherapy and every 4 weeks post-chemotherapy. Pregnancy test may occur on Day 1, but results must be available and reviewed by the treating physician or Investigator prior to commencing an infusion.
- h. Results for liver function tests, electrolytes, full blood count, and creatinine must be available before commencing an infusion (samples taken within 3 days prior to infusion) and reviewed by the treating physician or Investigator prior to dosing.
- i. Durvalumab will be administered first, followed by the etoposide + cisplatin/carboplatin regimen.
- j. If cisplatin, infuse over 1 to 2 hours. If carboplatin, infuse over 0.5 to 1 hour.
- k. Chemotherapy regimen (etoposide plus either cisplatin or carboplatin) to be administered Q3W for 4 to 6 cycles, per investigator clinical decision.
- l. See Section 6.1 and Appendix C for additional details relevant to image acquisition, RECIST 1.1 assessments, and evaluation of scans after RECIST 1.1-defined progression.
- m. Patients will have scans done Q6W for the first 12 weeks, and then Q8W thereafter or per institutional standard at investigator discretion.

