### **Efficacy assessments**

Tumour assessments will be performed as per RECISTv1.1 criteria, using computed tomography (CT)/magnetic resonance imaging (MRI). The baseline assessment is part of the screening procedures and should be performed before the start of study drug. Imaging assessment performed according to local standard clinical practice within 28 days before the first dose of study drug, but prior to signing the informed consent form (ICF), can be used for screening purposes if the patient consents to the use of those results. Efficacy for all patients will be assessed per investigator using objective tumour assessments according to RECIST v1.1 at week 6 $\pm$ 2 weeks, week 12 $\pm$ 2 weeks and Q8W  $\pm$ 2 weeks thereafter, until confirmed objective disease progression as defined by RECIST 1.1 (irrespective of the reason for stopping study drug and/or initiation of subsequent therapy). The schedule of imaging radiological assessments should be followed regardless of any dose delays.

The date, procedure, and overall response at each follow-up visit time-point will be documented, as well as if the patient is receiving benefit from the study medication. In case of disease progression, the physician will assess, date, and document the progression and methods (eg CT scan) used as per standard definitions and routine institutional standard of care.

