### **6.1 Efficacy assessments**

This study will evaluate the efficacy of durvalumab + EP as secondary endpoints, in terms of OS, as well as PFS, APF12, ORR, and DoR, which will be derived from site Investigator assessments per RECIST1.1.

Tumor assessments should utilize images from CT (preferred) or MRI, each preferably with IV contrast, of the chest and abdomen (including the entire liver and both adrenal glands), collected during screening/baseline and at regular (follow-up) intervals during study treatment. Any other areas of disease involvement should be additionally imaged based on the signs and symptoms of individual patients. It is important to follow the tumor assessment schedule as closely as possible (refer to the SoA, Table 2). Treatment continues until clinical progression/deterioration or confirmed radiological progression (refer to Section 8.2.1), and scanning/tumor assessments should continue throughout treatment until RECIST 1.1-defined radiological progression plus an additional follow-up scan (if clinically feasible).

The RECIST 1.1 guidelines (Appendix C) provide a method of assessment of change in tumor burden in response to treatment. Screening/Baseline imaging should be performed no more than 28 days before start of study treatment, and ideally should be performed as close as possible to and prior to the start of study treatment. The RECIST 1.1 assessments of baseline images identify Target Lesions (TLs) (defined as measurable) and Non-Target Lesions (NLTs). On-study images are evaluated for TLs and NLTs chosen at baseline, and for New Lesions (NLs) when they appear. This allows determination of follow-up TL response, NTL lesion response, the presence of unequivocal NLs, and overall timepoint responses (CR, PR, SD, PD, or Not Evaluable [NE]).

The date, procedure, and overall response should be documented at each follow-up visit timepoint as well as if the patient is taking benefit from the study medication. In case of disease progression, the physician will assess, date, and document the progression and methods (eg CT scan) used as per standard definitions and routine institutional standard of care.

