### **Progression free survival**

Progression-free survival is defined as the time from first dose of study treatment until the date of objective disease progression or death (by any cause in the absence of progression) regardless of whether the patient withdraws from study therapy or receives another anti-cancer therapy prior to progression. Patients who have not progressed or died at the time of analysis will be censored at the time of the latest date of assessment of investigator. However, if the patient progresses or dies after 2 or more missed visits, the patient will be censored at the time of the latest assessment. If the patient has no evaluable visits or does not have baseline data, they will be censored at the day of first dose unless they die within 2 visits of baseline. The PFS time will always be derived based on scan/assessment dates not visit dates.

The following rules will be applied:

- Date of progression will be determined based on the earliest of the dates of the component that triggered the progression.
- When censoring a patient for PFS, the patient will be censored at the latest of the dates contributing to a particular overall visit assessment.

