### **Tumor response evaluation**

#### **Schedule of evaluation**

The methods of assessment of tumor burden used at baseline CT/MRI scans of the chest and abdomen (including liver and adrenal glands) must be used at each subsequent follow-up assessment. Additional imaging may be performed based on the signs and symptoms of the patient, e.g., new lesions at follow up.

Baseline assessments should be performed no more than 28 days before start of study treatment, and ideally should be performed as close as possible to the start of investigational product. Efficacy for all patients will be assessed by objective tumor assessments every 6 weeks for the first 12 weeks, then every 8 weeks thereafter until confirmed objective disease progression as defined by RECIST 1.1 (irrespective of the reason for stopping treatment/or subsequent therapy). If an unscheduled assessment is performed, and the patient has not progressed, every attempt should be made to perform the subsequent assessments at their scheduled visits.

For patients who discontinue study drug due to toxicity in the absence of confirmed objective progression, objective tumor assessments should be continued every  $6\pm 2$  weeks for 12 weeks (relative to the date of randomization) then every  $8\pm 2$  weeks until confirmed objective disease progression.

Radiologic progression (PD by RECIST 1.1) requires confirmation; the confirmatory scan should occur no earlier than 4 weeks after the prior assessment of PD in the absence of clinically significant deterioration.

If progression is not confirmed then the patient should continue on study treatment continue with imaging assessments on their regular schedule.

If an unscheduled assessment was performed and the patient has not progressed, every attempt should be made to perform the subsequent assessments at their scheduled visits. This schedule is to be followed in order to minimise any unintentional bias caused by some patients being assessed at a different frequency than other patients.

Additional assessments will be performed post confirmed objective disease progression for patients remaining on IMT treatment, re-treatment, or until subsequent cancer therapy according to the clinical study protocol.

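### Table 2 footnote m leaves the scan interval after week 12 to local practice, contradicting the fixed 8-week schedule on which PFS, APF12 and DoR depend

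*Protocol*

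**What the plan says.** The tumour-assessment row of Table 2 (Section 5) reads: "On study tumor assessments should occur at Week 6±2 weeks, at Week 12±2 weeks then every 8±2 weeks". The superscript m sits on the 8-week part. Footnote m repeats six-weekly scans for the first 12 weeks and continues: "then Q8W thereafter or per institutional standard at investigator discretion".

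The other statements of the schedule offer no local alternative:

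- The synopsis (Efficacy assessments) gives week 6, week 12 and then every 8 weeks, each ±2 weeks, and adds: "The schedule of imaging radiological assessments should be followed regardless of any dose delays".
- Appendix C (Schedule of evaluation) requires scans "every 6 weeks for the first 12 weeks, then every 8 weeks thereafter until confirmed objective disease progression", and gives a reason: "This schedule is to be followed in order to minimise any unintentional bias caused by some patients being assessed at a different frequency".
- Section 6.1 asks sites to keep to the Table 2 schedule as closely as they can.

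The analysis rules in Section 9.4.2 build on scan dates. PFS is derived from scan or assessment dates, and a patient is censored at the latest assessment "if the patient progresses or dies after 2 or more missed visits". APF12 is the Kaplan-Meier estimate of PFS at 12 months. DoR ends on the PFS event date or uses the PFS censoring time.

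**The concern.** A site that follows footnote m can scan at any interval after week 12 and be compliant. A site that follows the row, the synopsis or Appendix C cannot. Both readings come from the current text, and no passage says which prevails.

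Two things are at stake. First, progression is recorded at the scan that finds it, so patients with the same disease course but different local intervals get different PFS and DoR times. Second, the missed-visit censoring rule needs an agreed list of expected visits. Without one, the same patient can be an event at one site and censored at another. In a single-arm study no control group shares the distortion. It could also enter the planned PS 0–1 and PS 2 subgroup results (Section 9.5.3) if discretion is used differently in frailer patients.

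**Working it through.** **The plan's own figure.** The protocol gives no figure for the effect of scan frequency. Its only design calculation, a Clopper-Pearson precision of 5.7% at 60% incidence with n = 300 (Section 9.2), reproduces as a half-width of 5.69%. It concerns the safety endpoint and is unaffected.

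**Missed visits.** Take a patient last scanned at week 12 who dies at week 31 with no scan between.

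- On the 8-week schedule, weeks 20 and 28 (windows closing at weeks 22 and 30) were missed. That is two visits, so the patient is censored at week 12.
- On a local 12-week schedule, only week 24 was missed, so the patient is a PFS event at week 31.

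**Detection delay and APF12 (illustration).**

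Inputs from Section 2.2.1.2, durvalumab + EP arm of the cited phase III trial: median PFS 5.1 months and 12-month PFS 17.5%. These are observed figures, used here as if they were the true curve.

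Assumptions not in the protocol: a Weibull shape, no deaths before progression, scans exactly on schedule, and local intervals after week 12 of 6, 10, 12 or 16 weeks.

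Model: S(t) = exp{−(t/λ)^k}.

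- k = ln[−ln 0.175 / ln 2] / ln(12/5.1) = ln(1.743/0.693) / ln(2.353) = 1.08
- λ = 5.1 / (ln 2)^(1/k) = 7.17 months = 31.2 weeks, at 52.18/12 weeks per month

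Progression is dated at the next scan, so recorded APF12 equals S at the last scan before 12 months (week 52.18). The recorded median is the first scan at which S is below 50%, where S(20) = 53.8%, S(22) = 50.3%, S(24) = 47.0% and S(28) = 41.0%. The true median is 22.2 weeks. Mean delay over all patients is by simulation.

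| Interval after week 12 | Last scan before 12 months | APF12 | Recorded median | Mean delay |
|---|---|---|---|---|
| 6 weeks | week 48 | 20.3% | week 24 | 3.1 weeks |
| 8 weeks (plan) | week 52 | 17.6% | week 28 | 3.8 weeks |
| 10 weeks | week 52 | 17.6% | week 32 | 4.6 weeks |
| 12 weeks | week 48 | 20.3% | week 24 | 5.4 weeks |
| 16 weeks | week 44 | 23.4% | week 28 | 7.0 weeks |

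Mean delay grows steadily with the interval. APF12 and the median do not, because they depend on where scans happen to fall. The largest APF12 shift is 23.4 − 17.6 = 5.8 points.

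**Deaths.** A death needs no scan, so the delay shrinks by the share of events that are deaths. With an assumed 30%, the 8-week delay is 3.8 × 0.7 = 2.7 weeks and the 12-week delay is 5.4 × 0.7 = 3.8 weeks, a difference of 1.1 weeks instead of 1.6.

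**The permitted window.** If every scan on the strict 8-week schedule is one week late, the last scan before 12 months is at week 45, and S(45) = 22.6%. That is 22.6 − 17.6 = 5.0 points from within the ±2-week allowance alone.

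**Scale.** Without censoring, the 95% half-width for APF12 at n = 300 is 1.96 × √(0.175 × 0.825/300) = 4.3 points.

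**The case against.** The strongest defence is that footnote m is itself a written statement of flexibility, in a Phase IIIb study whose primary aim is safety and whose efficacy analyses are descriptive. The synopsis sentence quoted above is about dose delays, and the Appendix C rationale follows a rule on unscheduled scans in a text that elsewhere refers to randomisation, which this trial does not have. Counting missed visits is often left to the SAP.

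Part of this stands. The endpoints affected are secondary, and no between-arm comparison can be biased. But if the flexibility is intended, then the Table 2 row, the synopsis and Appendix C are wrong instead, so the passages need reconciling either way. The Appendix C reason, "in order to minimise any unintentional bias caused by some patients being assessed at a different frequency than other patients", applies whatever causes the unequal frequency. An SAP can define a missed visit, but it cannot recover scans that were never done.

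Four stronger readings are tempting, and the documents do not support them:

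- **Longer intervals always inflate APF12.** The table shows otherwise: 6-weekly scanning gives the same 20.3% as 12-weekly, and 10-weekly gives no change.
- **The delay is 4.2 weeks against 6.4 weeks.** Those are the 8-weekly and 12-weekly means for events after week 12 only. Over all patients they are 3.8 and 5.4.
- **The whole scan schedule is waived.** The position of the superscript points to the phase after week 12, although the footnote's sentence could be clearer.
- **Results will be biased against the earlier phase III trial.** No passage plans a formal comparison, and that trial's scan schedule is not in the protocol.

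**Conclusion.** The contradiction is real and in current text: footnote m allows an unbounded local interval after week 12 where three other places require 8 weeks. PFS, APF12 and DoR would depend partly on local practice, and the missed-visit rule would lack a common reference.

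The numerical effect is moderate and its direction uncertain. Under the stated assumptions, moving everyone from 8-weekly to 12- or 16-weekly scans adds about 1.6 or 3.2 weeks of mean delay, and less if some events are deaths. APF12 shifts by 0 to about 6 points, against a sampling half-width of about 4.3. Real shifts would be smaller if only some sites departed from 8 weeks. The ±2-week window can cause APF12 shifts of similar size, so a shift of this size is not specific to footnote m. What the footnote adds is a departure without limits. The primary safety endpoints, OS and OS12 do not depend on scan timing.

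**What to change.** Delete the institutional-standard alternative from footnote m, so that one schedule applies throughout: week 6, week 12, then every 8 weeks, each ±2 weeks. State in Section 9.4.2 that missed visits are counted against that schedule.

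The change is one clause plus one clarifying sentence. The price is slightly less freedom for sites whose routine interval differs, and the existing window already absorbs small departures. The fix does not remove the dependence of APF12 on where scans fall within that window.
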